	
Number and percentage of maternal participants reporting pregnancy-related AESIs * and worsening of pre-existing medical conditions and/or obstetric complications from Day 1 up to 42 days post-delivery.
 
* These include maternal death, hypertensive disorders of pregnancy (gestational hypertension, pre-eclampsia, pre-eclampsia with severe features including eclampsia), fetal growth restriction, gestational diabetes mellitus, pathways to preterm birth (premature preterm rupture of membranes, preterm labor, provider-initiated preterm birth) and chorioamnionitis.
	
The number and percentage of maternal participants reporting each pregnancy-related AESI and worsening of pre-existing medical conditions and/or obstetric complications from Day 1 up to 42 days post-delivery will be tabulated with its exact 95% CI by group.
 
By participant listings of pregnancy-related AESIs and worsening of pre-existing medical conditions and/or obstetric complications will be prepared.

Infant participants	
Number and percentage of infant participants reporting neonatal / infant AESIs * from birth up to 42 days post-birth.
 
* These include small for gestational age, low birth weight including very low and extremely low birth weight (<2500 g, <1500g, <1000g), congenital anomalies (major external structural defects, internal structural defects, functional defects), neonatal death (in an extremely preterm birth [22≤GA<28 weeks], in a preterm live birth [28≤GA<37 weeks], or in a term live birth) and preterm birth.
	
The number and percentage of infant participants reporting each neonatal / infant AESI from birth up to 42 days post-birth will be tabulated with its exact 95% CI by group.
 
By participant listings of neonatal / infant AESIs will be prepared.

Primary Safety Endpoints		Statistical Analysis Methods
	Number and percentage of infant participants reporting SAE, (S)AEs leading to study withdrawal, and MAEs from birth up to 42 days post-birth.	The number and percentage of infant participants reporting: 
 at least one SAE at least one (S)AE leading to study withdrawal at least one MAE from Day 1 up to 42 days post-birth with exact 95% CIs will be tabulated by group and by MedDRA preferred term. By participant listings of SAEs, (S)AEs leading to study withdrawal and MAEs will be prepared.

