3. ANALYSIS SETS

3.1. Definition

Table 3 Maternal Participants

Analysis Set	Definition / Criteria	Analyses Evaluated
Enrolled	All maternal participants who completed the informed consent process and signed the informed consent form and were determined as eligible for study participation.	Study Population
Exposed	All maternal participants who received 1 dose of a study intervention. The allocation in a group is done in function of the administered intervention.	Safety
Full Analysis Immunogenicity	All maternal participants in the Exposed set who have at least one post-dosing immunogenicity data. It will be defined by timepoint, e.g. FAS at Day 31	Immunogenicity
Per-Protocol Immunogenicity	All maternal participants in the Full Analysis (Immunogenicity) minus participants with protocol deviations that lead to exclusion. The analysis will be done according to the study interventions that participants received. It will be defined by timepoint, e.g. PPS at Day 31.	Immunogenicity
Solicited Safety	All maternal participants in the Exposed set who have solicited safety data.	Safety

FAS = Full Analysis Set; PPS = Per Protocol Set

Table 4 Infant Participants

Analysis Set	Definition / Criteria	Analyses Evaluated
Exposed	Infants live-born to exposed maternal participants, whose parents/LARs completed the informed consent process and signed the informed consent form.	Safety
Full Analysis Immunogenicity	All infant participants in the Exposed set who have at least one post-delivery/birth immunogenicity data. The analysis will be done according to the study intervention that maternal participants received. It will be defined by timepoint, e.g. FAS at Day 31	Immunogenicity
Per-Protocol Immunogenicity	All infant participants in the Full Analysis (Immunogenicity) set minus those who (a) were born less than 4 weeks post-maternal participant dosing and/ or (b) have protocol deviations that lead to exclusion. It will be defined by timepoint, e.g. PPS at Day 31	Immunogenicity

FAS = Full Analysis Set; PPS = Per Protocol Set

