4.2. Primary Endpoint(s) Analyses

4.2.1. Safety

4.2.1.1. Analysis of safety and reactivity planned in the protocol

Safety analyses in maternal participants will include summaries by study group and age category (<18 years; ≥ 18 years; overall) of solicited administration site and systemic events, unsolicited AEs, MAEs, SAEs, MA-RTIs, RSV-associated MA-RTIs, (S)AEs leading to study withdrawal, worsening of pre-existing medical conditions and/or obstetric complications, pregnancy outcomes and pregnancy-related AESIs.

Safety analyses in infant participants will include summaries by study group and gestational age at birth (≥ 37 weeks; <37 weeks; overall) of neonatal AESIs, MAEs, SAEs, (S)AEs leading to study withdrawal, and occurrence of RSV- associated LRTIs, severe LRTIs, RSV-associated hospitalization.

The reactivity analysis will be performed on Solicited Safety Set for maternal participants, and other safety analyses will be performed on the Exposed Sets for both maternal and infant participants.

	Primary Safety Endpoints	Statistical Analysis Methods
Maternal participants	Number and percentage of maternal participants reporting solicited administration site and systemic events during a 7-day (i.e. Day 1 to Day 7 included) follow-up period after dosing.	
The number and percentage with exact 95% CI of maternal participants reporting each solicited administration site event (any grade, each grade,) and solicited systemic event (any, each grade) during the 7-day (7 days post-study intervention, Day 1 included) follow-up period after dosing will be tabulated by maximum intensity per participant for each study group.
 
The number and percentage of maternal participants reporting:
 
 • at least one administration site AE (solicited and unsolicited) • at least one systemic AE (solicited and unsolicited) • any AE 
during the 7-day (7 days post-study intervention, Day 1 included) follow-up period after dosing will be tabulated with exact 95% CI by group.
 
The same computations will be done for Grade 3 solicited and unsolicited AEs, for any unsolicited AEs considered related to study intervention, for any Grade 3 unsolicited AEs considered related to study intervention and for any solicited and unsolicited AEs resulting in a medically attended visit (i.e., MAEs).

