	
Number and percentage of maternal participants reporting pregnancy-related AESIs * and worsening of pre-existing medical conditions and/or obstetric complications from Day 1 up to 42 days post-delivery. * These include maternal death, hypertensive disorders of pregnancy (gestational hypertension, pre-eclampsia, pre-eclampsia with severe features including eclampsia), fetal growth restriction, gestational diabetes mellitus, pathways to preterm birth (premature preterm rupture of membranes, preterm labor, provider-initiated preterm birth) and chorioamnionitis.
	
The number and percentage of maternal participants reporting each pregnancy-related AESI and worsening of pre-existing medical conditions and/or obstetric complications from Day 1 up to 42 days post-delivery will be tabulated with its exact 95% CI by group.
 
By participant listings of pregnancy-related AESIs and worsening of pre-existing medical conditions and/or obstetric complications will be prepared.

CONFIDENTIAL

	Primary Safety Endpoints	Statistical Analysis Methods
Infant participants	
Number and percentage of infant participants reporting neonatal / infant AESIs * from birth up to 42 days post-birth.
 
* These include small for gestational age, low birth weight including very low and extremely low birth weight (<2500 g, <1500g, <1000g), congenital anomalies (major external structural defects, internal structural defects, functional defects), neonatal death (in an extremely preterm birth [22<GA<28 weeks], in a preterm live birth [28<GA<37 weeks], or in a term live birth) and preterm birth.
	
The number and percentage of infant participants reporting each neonatal / infant AESI from birth up to 42 days post-birth will be tabulated with its exact 95% CI by group.
 
By participant listings of neonatal / infant AESIs will be prepared.

	
Number and percentage of infant participants reporting SAE, (S)AEs leading to study withdrawal, and MAEs from birth up to 42 days post-birth.
	
The number and percentage of infant participants reporting:
 
 • at least one SAE • at least one (S)AE leading to study withdrawal • at least one MAE 
from Day 1 up to 42 days post-birth with exact 95% CIs will be tabulated by group and by MedDRA preferred term.
 
By participant listings of SAEs, (S)AEs leading to study withdrawal and MAEs will be prepared.

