4.2.1.2. Additional considerations

Refer to Section [4.3.1.2](#)

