4.3.1.2.4. Analysis of pregnancy outcome

The analysis of pregnancy outcome will be performed on Exposed Set.

Still births, preterm births and spontaneous abortions will be counted per pregnancy, regardless of the number of fetuses in the concerned pregnancy.

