4.8. Changes to Protocol Defined Analyses

The distribution analysis for antibody titers/concentration and scatter plots for individual immunogenicity data, which were originally planned statistical analysis specified in the protocol Amendment 1 (Dated: 15-MARCH-2022), are removed from this SAP as the sufficient relevant information has been obtained from other RSV MAT Phase I/II studies.

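### With twins eligible, the SAP leaves two counting rules for preterm birth (per infant and once per pregnancy) without saying which table each governs, and the per-infant exact interval ignores co-twin concordance

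*SAP*

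**What the plan says.** Protocol 5.1.1 admits adults with an uncomplicated twin gestation, and protocol 5.2.1.1 excludes three or more fetuses. An enrolled pregnancy can therefore yield one or two infants. The infant Exposed Set (SAP 3.1, Table 4) consists of "Infants live-born to exposed maternal participants, whose parents/LARs completed the informed consent process and signed the informed consent form", so both live-born, consented co-twins enter it.

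Two rules then bear on preterm birth.

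- **Per infant.** SAP 4.2.1.1 names preterm birth among the neonatal AESIs and takes the infant as the unit of that row, split by study arm: "infant participants reporting each neonatal / infant AESI from birth up to 42 days post-birth will be tabulated with its exact 95% CI". Protocol 9.4.3.1 has the same unit: the "percentage of infant participants reporting each neonatal / infant AESI from birth up to 42 days post-birth will be tabulated". SAP 4.1.1 specifies Clopper-Pearson for proportions.
- **Per pregnancy.** SAP 4.3.1.2.4 states: "Still births, preterm births and spontaneous abortions will be counted per pregnancy, regardless of the number of fetuses in the concerned pregnancy". It also says that "The analysis of pregnancy outcome will be performed on Exposed Set".

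SAP 4.2.1.2 refers the reader of the primary safety section to SAP 4.3.1.2, which contains the per-pregnancy rule. SAP 4.2.1.1 says that "other safety analyses will be performed on the Exposed Sets for both maternal and infant participants", so the single Exposed Set named in 4.3.1.2.4 could be either one. SAP 4.8 lists as changes from the protocol only "The distribution analysis for antibody titers/concentration and scatter plots for individual immunogenicity data"; it does not mention a counting unit.

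**The concern.** A preterm twin delivery with two live-born infants adds two events under one rule and one under the other. Once a single such delivery occurs, the two rules give different numerators. The per-pregnancy rule comes with no denominator, so a programmer could also set a pregnancy count over infants.

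The rate will be read closely: protocol 2.3 records that an imbalance in preterm births in RSV MAT-009 led to the enrolment pause. The study is also fully unblinded (protocol 6.3.5), so a unit left to the programming stage would be chosen when group results can be seen.

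A second issue follows if the per-infant row stands. Co-twins normally share a gestational age at birth and so are nearly always both preterm or both term. A plain Clopper-Pearson interval treats them as independent.

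**Working it through.** **Which event each rule governs.** The nine pregnancy outcomes in SAP 4.2.1.1 are live birth, fetal death or stillbirth, and termination, each split by anomaly status. Preterm birth is not among them. As an endpoint it appears only as a neonatal AESI. The maternal AESI on pathways to preterm birth is a different endpoint, counted per mother. So the preterm-birth wording in 4.3.1.2.4 either applies to the neonatal AESI, where it conflicts with the row's unit, or applies to a maternal display that the SAP does not define.

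**Check of the interval routine against the plan.** SAP 5.1 gives 72%, 92% and 98% for at least one event in 252. 1 − (1 − p)^252 gives 71.7%, 92.1% and 97.8% at p = 0.5%, 1% and 1.5%. The Clopper-Pearson upper limit for 0/252 is 1.45%, stated as 1.5%. Both reproduce.

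**Effect on the rate.** The documents give no twin share, no preterm risks and no final sample size, so all inputs are assumptions. 252 is the planned vaccine arm. Take 25 twin pregnancies (227 + 2 × 25 = 277 infants), all infants live-born and consented, co-twins concordant, and 23 of 227 singleton pregnancies preterm.

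| Twin pregnancies preterm | Per infant (exact 95% CI) | Per pregnancy (exact 95% CI) | Pregnancy count over infants |
|---|---|---|---|
| 8 of 25 | (23 + 16)/277 = 14.1% (10.2–18.7) | (23 + 8)/252 = 12.3% (8.5–17.0) | 31/277 = 11.2% |
| 12 of 25 | (23 + 24)/277 = 17.0% (12.7–21.9) | (23 + 12)/252 = 13.9% (9.9–18.8) | 35/277 = 12.6% |

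The per-infant and per-pregnancy intervals overlap.

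**Effect on the per-infant interval.** With S singleton and T twin pregnancies and concordant pairs, the infant count is X = Bin(S, p₁) + 2·Bin(T, p₂), with n = S + 2T. Coverage is the exact probability that the Clopper-Pearson interval for X/n contains (S·p₁ + 2T·p₂)/n. With equal risk the variance ratio to the binomial is (S + 4T)/n. At T = 25 this is 327/277 = 1.18, a standard-error ratio of 1.09. For 252 mothers:

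| Twin share (T) | Equal 10% risk | 30% twin vs 10% singleton risk |
|---|---|---|
| 5% (13) | 95.0% | 93.5% |
| 10% (25) | 94.8% | 92.6% |
| 20% (50) | 93.4% | 90.6% |
| 30% (76) | 90.5% | 88.3% |

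The per-pregnancy exact interval covers 96.1–97.1% across these scenarios.

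**What a clustered interval does.** For 39/277, r = 0.1408. With y the number of preterm infants and m the number of infants per mother, Σ(y − r·m)² = 23(0.859)² + 204(0.141)² + 8(1.718)² + 17(0.282)² ≈ 46.0. Multiplying by 252/251 and dividing by 277² gives 0.000602, against a binomial 0.1408 × 0.8592/277 = 0.000437. The design effect is 1.38 and the effective sample size 277/1.38 ≈ 201. Clopper-Pearson at that size (Korn-Graubard) gives 9.6–19.7%, against 10.2–18.7% unclustered.

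**The case against.** The best defence is that there is no conflict. SAP 4.3.1.2.4 is headed as a pregnancy-outcome analysis, pregnancy outcomes are tabulated per mother, and neonatal AESIs have their own per-infant row. Its sentence also names spontaneous abortions, which are in neither endpoint list, so it reads as a generic counting rule rather than one written for the AESI table. The cross-reference in 4.2.1.2 covers several subsections and does not mention neonatal AESIs. Protocol and SAP agree on the per-infant unit, and SAP 4.8 declares no departure.

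Much of this stands. A reader might infer that the per-pregnancy rule overrides the primary AESI row, or that no unit governs at all. The documents support neither: per infant is the better-supported reading. What the defence leaves open is where a per-pregnancy count of preterm births belongs, since no pregnancy outcome or maternal table for it is defined, and what it is divided by.

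A reader might also infer that the choice of unit creates or hides a difference between arms. Under randomisation a change of unit shifts both arms in the same direction in expectation, and no hypothesis is tested (SAP 2).

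It is also fair that every magnitude here is assumed, that enrolment stopped before the planned size was assured, and that the larger coverage losses need a high twin share or a higher risk in twins.

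**Conclusion.** The point holds as an ambiguity that the SAP should close, with per infant as the default. One event has two counting rules, and the text does not assign each to a table or give the second a denominator. Under the stated assumptions the choice moves the reported rate by 1.8 points (14.1% vs 12.3%) or 3.1 points (17.0% vs 13.9%).

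The interval issue is secondary. With fully concordant pairs and 252 mothers, the loss of coverage is negligible at 5–10% twins with equal risk. Coverage is about 93% at 5–10% twins with 30% versus 10% risk, and about 88–93% at 20–30% twins. The consequence is confined to a descriptive rate and its interval. It merits correction before the analysis is run because preterm birth is one of the events behind the programme's safety signal.

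**What to change.** 1. In SAP 4.2.1.1, keep the protocol's per-infant row for preterm birth, but replace the plain Clopper-Pearson interval for that row with a mother-clustered one, for example Korn-Graubard. List this in SAP 4.8.
2. In SAP 4.3.1.2.4, state that the per-pregnancy count of preterm births is a separately labelled display that does not replace the neonatal AESI row. Give it its own denominator, for example exposed mothers with at least one live-born infant in the infant Exposed Set, and an exact 95% CI by group.
3. If the sponsor prefers per pregnancy as the primary unit, declare that in SAP 4.8 as a change from protocol 9.4.3.1.

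The cost is one extra table row, two short SAP edits and a somewhat wider per-infant interval (10.1 against 8.5 points in the 39/277 example). Mother and infant identifiers are already linked (protocol 6.3.1), so no new data are needed. The per-pregnancy interval can be slightly narrower or wider than the unclustered per-infant one: on average 8.08 against 8.14 points at 5% twins with 30% versus 10% risk, and 7.8 against 7.4 at 10% twins with equal risk.

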4.2.1.2. Additional considerations

Refer to Section [4.3.1.2](#)

4.2.2. Immunogenicity

4.2.2.1. Analysis of immunogenicity planned in the protocol

The primary analysis for immunogenicity will be based on the PPS for analysis of immunogenicity.

	Primary Immunogenicity Endpoints	Statistical Analysis Methods
Maternal participants	
 • Humoral immune responses at pre-dosing (Day 1) and at delivery: 
 – RSVPreF3 IgG-specific antibody concentrations – Neutralizing antibody titers against RSV-A 	
For each assay, at each timepoint and by study group and age category (<18 years; ≥ 18 years; overall):
 
 • Antibody titers/concentrations will be displayed using reverse cumulative curves. • GMTs/ GMCs will be tabulated with 95% CI and represented graphically. • GMR of antibody titers/concentrations at delivery over pre-dosing will be tabulated with 95% CI. 
Between group evaluation in terms of RSVPreF3 IgG-specific antibody concentrations and neutralizing antibody titers against RSV-A will be performed at delivery using an ANCOVA model on the logarithm₁₀ transformation of the concentrations/titers, and including the pre-dosing logarithm₁₀ transformation of the concentrations/titers, the study intervention, gestational age at the time of study intervention administration (<28^{0/7}; ≥ 28^{0/7} weeks), and the interval between dosing and delivery as covariates if needed.

Cord blood/placental transfer	
Ratio between cord blood* and maternal RSVPreF3 IgG-specific antibody concentrations at delivery.
 
*or infant blood sample collected within 72 hours after birth (if no cord blood sample can be obtained).
	
 • Geometric mean of placental transfer ratio will be tabulated with 95% CI by study group. • Percentage of infants with placental transfer ratio ≥ 1 will be tabulated with exact 95 % CI by study group.

	Primary Immunogenicity Endpoints	Statistical Analysis Methods
Infant participants	
 • Humoral immune responses at delivery*: 
 – RSVPreF3 IgG-specific antibody concentrations – Neutralizing antibody titers against RSV-A 
*Measured in cord blood sample collected at delivery or infant blood sample collected within 72 hours after birth (if no cord blood sample can be obtained).
	
For each assay, the following analysis will be performed by study group
 
 • Antibody titers/concentrations will be displayed using reverse cumulative curves. • GMTs/ GMCs will be tabulated with 95% CI and represented graphically. 
Between group evaluation in terms of RSVPreF3 IgG-specific antibody concentrations and neutralizing antibody titers against RSV-A will be performed at delivery using an ANCOVA model on the \log_{10} transformation of the concentrations/titers, and including the pre-dosing \log_{10} transformation of the concentrations/titers, the study intervention, gestational age at the time of study intervention administration ($<28^{0/7}$; $\geq 28^{0/7}$ weeks), and the interval between dosing and delivery as covariates if needed.
 
In addition, if cord blood samples are missing in 20% or more of infants in a single study group, and if the data permit: RSV antibody concentrations/titers in infants through time will be evaluated separately in infants with cord blood samples and in infants from whom, instead, a blood sample was obtained within 72 hours after birth.

ANCOVA = Analysis of covariance; **CI** = Confidence interval; **GMR** = Geometric mean of ratio; **GMT/ C** = Geometric mean titer/ concentration; **RSV-A** = Respiratory syncytial virus subtype A; **RSVPreF3 IgG** = Respiratory syncytial virus PreF3 immunoglobulin G

4.2.3. Sensitivity analyses

Refer to Section [4.3.3](#)

4.3. Secondary Endpoint(s) Analyses

4.3.1. Safety

4.3.1.1. Analysis of safety and reactogenicity planned in the protocol

Safety analyses in maternal participants will include summaries by study group and age category (<18 years; ≥ 18 years; overall) of solicited administration site and systemic events, unsolicited AEs, MAEs, SAEs, MA-RTIs, RSV-associated MA-RTIs, (S)AEs leading to study withdrawal, worsening of pre-existing medical conditions and/or obstetric complications, pregnancy outcomes and pregnancy-related AESIs.

Safety analyses in infant participants will include summaries by study group and gestational age at birth (≥ 37 weeks; <37 weeks; overall) of neonatal AESIs, MAEs, SAEs, (S)AEs leading to study withdrawal, and occurrence of RSV- associated LRTIs, severe LRTIs, RSV-associated hospitalization.

CONFIDENTIAL

The reactogenicity analysis will be performed on Solicited Safety Set for maternal participants, and other safety analyses will be performed on the Exposed Sets for both maternal and infant participants.

	Secondary Safety Endpoints	Statistical Analysis Methods
Maternal participants	Number and percentage of maternal participants reporting SAEs, (S)AEs leading to study withdrawal and MAEs from Day 1 up to 180 days post-delivery.	The number and percentage of maternal participants reporting: 
 at least one SAE at least one (S)AE leading to study withdrawal at least one MAE from Day 1 up to 180 days post-delivery with exact 95% CIs will be tabulated by group and by MedDRA preferred term. By participant listings of SAEs, (S)AEs leading to study withdrawal and MAEs will be prepared.
	Number and percentage of maternal participants reporting worsening of pre-existing medical conditions and/or obstetric complications from Day 1 up to 180 days post-delivery.	The number and percentage of maternal participants reporting each worsening of pre-existing medical conditions and/or obstetric complications from Day 1 up to 180 days post-delivery will be tabulated with its exact 95% CI by group. By participant listings of worsening of pre-existing medical conditions and/or obstetric complications will be prepared.
	Number and percentage of maternal participants reporting RSV-associated MA-RTIs from Day 1 up to 180 days post-delivery.	The number and proportion of participants reporting at least one RSV-associated MA-RTI from Day 1 up to 180 days post-delivery with exact 95% CIs will be calculated and tabulated.
Infant participants	From birth up to 365 days post-birth (12 months of age), number and percentage of infant participants reporting medically assessed, RSV-associated LRTIs of any severity and severe RSV-associated LRTIs (according to the case definitions).	The number and percentage of infant participants reporting: 
 at least one medically assessed, RSV-associated LRTI of any severity at least one medically assessed, severe RSV-associated LRTI from birth up to 365 days post-birth (12 months of age) will be calculated and tabulated by group.
	From birth up to 365 days post-birth (12 months of age), number and percentage of infant participants reporting medically assessed, RSV-associated hospitalizations (according to the cases definitions).	The number and percentage of infant participants reporting at least one medically assessed, RSV-associated hospitalization from birth up to 365 days post-birth (12 months of age) will be calculated and tabulated by group.

AE = Adverse event; **LRTI** = Lower respiratory tract illness; **MAE** = medically attended adverse event; **NB** = Newborn; **RSV-MA-RTI** = respiratory syncytial virus associated medically attended respiratory tract illness; **SAE** = serious adverse event

